6.5.3 Breaking the Blind

Treatment assignment may be revealed only for reasons relating to the participant's safety or when critical therapeutic decisions are contingent on knowing the assigned study medication. Except in the most pressing circumstances, a decision to break the blind must be discussed with the Operations Center, Chair of the Protocol Committee or the Chair's designee from the Protocol Committee and permission in writing must be obtained before the blind may be broken. Withdrawal of a participant from the study is not a sufficient reason to break the study blind.

If the blind is broken, the pharmacist will record key information at the time the blind is broken. Information to be collected includes the participant number and initials, medication kit number, date the blind was broken, reason for breaking the blind, the name of the investigator who requested the blind be broken, the name of the pharmacist who broke the blind, and the names of the Clinical Review Committee members who authorized breaking the blind. A member of the Clinical Review Committee will fax or e-mail written permission to break the blind to the pharmacist and to the Operations Center.

6.6 Modifications for Toxicity

Participants who experience grade 2 toxicity related to Lovastatin will have Lovastatin withheld until the toxicity resolves (grade ≤ 1) and then restarted at the same dose level. If the grade 2 toxicity recurs, the dose will be withheld again until the toxicity resolves (grade ≤ 1) and then reduced to 50% of the dose. If the grade 2 toxicity recurs, the participant will be taken off the protocol. The participant will be evaluated by the principal investigator.

Participants who experience grade 3 or 4 toxicity related to Lovastatin will have their dose withheld. If the toxicity returns to grade ≤ 1 within 10 days, the participant may resume Lovastatin at a dose reduced by 50%. If the toxicity persists at grade ≥ 2 for >10 days without administration of Lovastatin or the grade 3 or 4 toxicity recurs at the lower dose, the participant will be removed from the study.

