3.0 Research Design and Methods

3.1 Study Design

This is a prospective multi-center; randomized, placebo-controlled Phase II study to determine the efficacy of Lovastatin on visual spatial learning and/or attention abilities of children with NF1 aged 8 to less than 16 years. In addition, the effect of Lovastatin on secondary measures of executive function, visual spatial skills, behavior and quality of life will be assessed. Participants will be randomized to 16-weeks of treatment with Lovastatin or a matched placebo. It is plausible and ethical to employ a placebo group as no standard therapy with established efficacy is being withheld. There is no cross-over in this study due to a lack of data concerning the length of possible washout effects. The Lovastatin dose will begin at 20 mg once daily/continuous dosing and escalate over a two-week period to 40 mg once daily/continuous dosing and continue at this dose for 14 weeks. Participants will be carefully monitored for side effects. The safety of Lovastatin will be evaluated using laboratory tests, clinical signs and adverse effects, which will be monitored at regular intervals over the 16-week period. Primary and secondary outcome measures will be administered at baseline, 16 weeks post-treatment and at follow-up, 8 weeks after cessation of treatment to determine any carry-over effects. The safety of Lovastatin will also be evaluated, with regular monitoring of side-effects during the trial.

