5.2 Treatment Visits

5.2.1 Dose Schedule and Prescription

Eligible participants will be dispensed 20mg of Lovastatin or the placebo at the initiation of treatment. Participants will be given directions to take the medication once daily after dinner time. Given that Lovastatin has a strong odor; participants will be required to swallow the capsule whole without breaking the seal. Participants will take one tablet (20mg Lovastatin) per dose for two weeks; and increase to two tablets per dose during the following weeks (40 mg Lovastatin). Participants will continue on the same dosage for a total of 14 weeks. In order to assess medication compliance, participants will be required to complete pill diary forms. All participants will be provided with a complete list of medications and products that have detrimental interactions with Lovastatin that must be completely avoided while being treated with Lovastatin (see Appendix 6).

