6.3 Procedures/Recommendations for Drug Supply and Distribution

Lovastatin and its matching placebo will be obtained and distributed to participating sites by a subcontractor to the Operations Center. A 20mg tablet of Lovastatin or an identical tablet (placebo) will be provided for each participant. Medications, including the placebo, will be provided to the participants free of charge. Participants will be instructed to return all unused medications as well as empty bottles at each clinic visit. All unused medicine will be disposed of properly at each individual site.

Lovastatin is administered orally. The bioavailability of the tablet increases under the influence of a meal. Based on these findings, it is advised to take the tablets immediately after a meal. One dose per day after dinner time will be instructed to parents, since evening doses are more effective than the same dose given in the morning (Merck & Co., Inc, 2007). Lovastatin is a substrate for cytochrome P450 isoform 3A4 (CYP3A4). Grapefruit juice contains one or more components that inhibit CYP3A4 and can increase the dose concentration. Participants will be instructed to avoid the consumption of grapefruit juice during the treatment. A complete list of drug interactions/contraindications will be described to parents and participants.

Compliance will be monitored by recording the number of pills dispensed to families from the pharmacy and then comparing that to the number of pills that are returned at each monthly visit. Participants will be asked to return all unused pills at each visit. A pill diary will also be maintained by each participant and reviewed at each follow-up visit to ensure compliance with the medication.

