6.4 Drug Dosage and Possible Interactions

The selection of the maximum dose of Lovastatin to be used in this study, 40 mg/day, is based on the tolerability of the drug when used for heFH and the results of the Phase I study examining safety and tolerability of Lovastatin in children with NF1 (Acosta et al., submitted). Participants will commence at 20 mg/day for two weeks and escalate to the 40 mg/day dose in week 3.

Approximately 40% of children with NF1 are diagnosed with comorbid ADHD, many of whom are treated with psychostimulant medication such as methylphenidate and/or dextroamphetamines. In order to minimize recruitment bias and ensure recruitment targets are met, patients taking methylphenidate and/or dextroamphetamines will be eligible for this study.

The predominant metabolic pathway of methylphenidate is de-esterification to form pharmacologically inactive d- or l-ritalinic acid (Patrick et al 1987). Metabolism of methylphenidate when used by oral administration undergoes a stereoselective clearance to ritalinic acid (CES1A1 is the major enzyme responsible) before entering systemic circulation (Sun et al, 2004). Methylphenidate does not use the microsomal cythochrome P450 in the liver for its metabolism (Sun et al 2004; Patrick et al 1987). Dextroamphetamines are metabolized by the cythochrome P450 in liver. However the isoenzyme responsible for its metabolism is the CYP2D6 (Adderall Medication Guide, Shire, Nov. 2010). Instead, lovastatin is metabolized by the CYP3A4 (Ritalin® Medication Guide, Novartis, 2010). There are not described interactions or competitive mechanism between dextroamphetamines and lovastatin.

Although limited by a small sample size, results of the Phase I study provide some evidence for the inclusion of patients on stimulant medication (Acosta et al., submitted). A total of 23 patients with NF1 (10-17 years of age) completed 12 weeks of treatment with Lovastatin. Nine patients had a diagnosis of ADHD and five of these patients were taking a stable dose of stimulant medication during the course of the study. Calculation of Reliable Change Index for individuals indicated significant improvements on both verbal and nonverbal memory measures in approximately 40% of participants regardless of whether they were off or on methylphenidate.

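### The 50% dose-reduction rule in 6.6 cannot be carried out for a child on 20 mg, and no section says what happens to the week-3 step-up after toxicity in weeks 1-2

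*Protocol*

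**What the plan says.** **Schedule.** Section 3.1: "The Lovastatin dose will begin at 20 mg once daily/continuous dosing". Section 5.2.1 gives the unit count: "one tablet (20mg Lovastatin) per dose for two weeks; and increase to two tablets per dose during the following weeks (40 mg Lovastatin"), and then "Participants will continue on the same dosage for a total of 14 weeks". Section 6.4 repeats the timing: "Participants will commence at 20 mg/day for two weeks and escalate to the 40 mg/day dose in week 3". None of these attaches a condition to the increase.

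**Supply.** Section 6.3: "A 20mg tablet of Lovastatin or an identical tablet (placebo) will be provided for each participant". Section 5.2.1 adds, because of the drug's odor, that "participants will be required to swallow the capsule whole without breaking the seal". It calls the unit a capsule there and a tablet in the next sentence. No other strength and no dosing interval other than daily is described.

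**Toxicity.** Under section 6.6 a first related grade 2 event means "Lovastatin withheld until the toxicity resolves (grade ≤ 1) and then restarted at the same dose level". A recurrence means a second hold and then half the dose; a further recurrence takes the child off protocol. For related grade 3 or 4 events the drug is withheld, and "If the toxicity returns to grade ≤ 1 within 10 days, the participant may resume Lovastatin at a dose reduced by 50" percent. If the event does not settle within that time, or recurs at the lower dose, the child is removed. Section 6.11 refers participants with drug-related adverse events to 6.6 for withholding or modification. The SAP has nothing on dose modification.

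**The concern.** Section 6.6 defines its actions relative to the dose the child is taking, and that dose is not always 40 mg. Every child is on 20 mg in weeks 1-2, and a child already reduced stays on 20 mg. From there the rule asks for an amount that the described supply cannot provide.

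The second problem is one of sequence. Section 6.6 says what to do at the event, and 5.2.1 and 6.4 say what everyone does in week 3, but nothing connects them. A child held, restarted or reduced in weeks 1-2 reaches the step-up date with no stated instruction.

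At stake are the safety of the affected children and consistency between sites in delivered dose and in removals for toxicity. The trial enrols 8- and 9-year-olds, for whom 4.1 and 6.11 acknowledge a lack of preliminary safety data.

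**Working it through.** **Inputs.** Unit 20 mg (6.3), swallowed whole (5.2.1), once daily (3.1); one unit for 2 weeks, then two (5.2.1, 6.4); 50% reduction and a 10-day limit on recovery from grade 3 or 4 events (6.6).

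**The plan's own schedule reproduces.** 1 × 20 = 20 mg; 2 × 20 = 40 mg; 2 + 14 = 16 weeks.

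**The 50% rule at each dose level.** Units needed = (0.5 × current dose) / 20.

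| Current dose | 50% of it | Units | Deliverable as described? |
|---|---|---|---|
| 40 mg | 20 mg | 1.0 | yes |
| 20 mg | 10 mg | 0.5 | no |

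**Who is on 20 mg when the rule applies.**
- A child with a related grade 3 or 4 event in weeks 1-2.
- A child with a recurrent related grade 2 event in weeks 1-2. Onset, hold, resolution, restart and recurrence must all fit within 14 days, so this is the rarer route.
- A child already reduced to 20 mg who then has a different grade 3 or 4 toxicity. If the same toxicity returns, 6.6 takes the child off, so the second halving clearly arises only for a different one.

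**Overlap with the step-up.** If a hold starts on day d and lasts the full 10 days, dosing resumes on day d + 10. This is later than day 14 when d ≥ 5, so such a hold starting on any of days 5-14 reaches or crosses the step-up date.

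**Dose in week 3 after toxicity in weeks 1-2.**

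| State entering week 3 | If the step-up does not apply | If the step-up is applied literally |
|---|---|---|
| Still on hold | 0 mg | 40 mg |
| Grade 2, restarted at the same level | 20 mg | 40 mg |
| Reduced by 50% | 10 mg (not deliverable) | 40 mg |

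In the second row the readings differ by 40/20 = 2-fold. The third row compares 40 mg with a dose that cannot be dispensed, so its ratio is not a useful measure of size.

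**How many children.** Section 6.5.2 gives frequencies, but not by grade or week. Assuming equal allocation, 142/2 = 71 children receive lovastatin. Muscle pain, skin redness, nausea, abdominal pain and headache are listed as rare (0.01% to 0.1%): 71 × 0.0001 = 0.007 to 71 × 0.001 = 0.07 expected cases per listed event, at any grade. Constipation and dyspepsia are common (1% to 10%): 0.7 to 7 cases each, at any grade. Only events that reach grade 2 or above, are judged related and occur at 20 mg matter here. The listing is a rough guide, since 6.11 names muscle pain and gastrointestinal symptoms among the most frequent effects. Appendix 3 schedules no on-treatment laboratory test before week 4, so events seen in weeks 1-2 would be mainly symptomatic.

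**The case against.** **Section 6.6 already governs.** A reader might infer that 6.6 and the step-up contradict each other outright, with 10 mg set against 40 mg. The documents do not support that. Section 6.11 sends children with related toxicity to 6.6, and the heading of 5.2.3 points there too, so the calendar is the default and 6.6 the exception for the hold or reduction itself. What survives is a silence: 6.6 never mentions the step-up and gives no duration for the restarted dose.

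**Resumption after grade 3 or 4 is optional.** The wording is permissive, the Clinical Review Committee reviews grade 3 to 5 events (6.8), and a child may be taken off in his or her best interest (5.2.3). So it goes too far to say that every site must improvise. These provisions assign review and allow stopping, but none supplies a deliverable reduced dose. For recurrent grade 2 the halving is not optional.

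**Half might mean half of the full 40 mg.** A child on 20 mg would then resume on 20 mg, which is no reduction, although 6.6 goes on to speak of recurrence at a lower dose.

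**There is a check at the step-up.** This is correct: Appendix 3 marks the toxicity checklist and drug compliance at the 2-week phone call. The call may detect toxicity, but no text says what then happens to the increase.

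**Muscle events have their own rule.** Section 6.5.2 requires discontinuation if myopathy is diagnosed or suspected, so some cases never reach the 50% rule. This stands and narrows the group.

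**Conclusion.** The point holds as a gap in the wording. The 50% rule fails at 20 mg under the supply described, and the effect of toxicity in weeks 1-2 on the week-3 increase is not stated. Read literally, 5.2.1 and 6.4 double the dose of a child recently restarted on 20 mg. The arithmetic is certain. The conclusion assumes that no other strength or dosing interval exists outside the documents.

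The number affected is probably small. All 142 participants pass through the 20 mg phase (2/16 = 12.5% of treatment time), but that counts exposure, not affected children. Sample size, alpha and power are unaffected.

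A reader might go on to infer that opening a unit would unmask treatment, or that the inconsistency would fall mainly on the lovastatin arm. Neither is established. Section 5.2.1 links whole swallowing to odor without mentioning masking, and nothing says whether the placebo smells. An imbalance between arms would require toxicity judged related to be more common on lovastatin. Both remain conditional. The case for changing the text rests on safety, consistency between sites and low cost.

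**What to change.** Reconcile 5.2.1, 6.3, 6.4, 6.6 and 6.11 on three matters:

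- For each state in which toxicity can occur (before the step-up, at full dose, after an earlier reduction), 6.6 should give an action that can be carried out with the units supplied.
- State how 6.6 acts on the week-3 step-up for a child held, restarted or reduced in weeks 1-2: cancelled, delayed or kept.
- Express each action as a number of units, the same in both arms, so that masked staff and the pharmacy follow one instruction. Use one term for the unit, which 5.2.1 calls both a capsule and a tablet.

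The clinical team decides the content; no dose or clinical rule is proposed here. The cost is protocol wording and a line in the pharmacy instructions, with no extra visits or tests.

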6.7 Adverse Event Monitoring (UK sites please refer to Appendix 10)

Participants will be monitored closely for medication side effects with a diary and with laboratory testing as indicated in the Study Procedures section (see of the protocol (see Section 5). Adverse events will be addressed immediately as described in Section 6.8. Participants will also be closely followed clinically at least once per month while on the study medication by the site physician. The Side Effects Checklist and Adverse Event Monitoring Form will be used to assess participants at every visit or phone contact.

Participants will be monitored for adverse events regularly throughout the study. Adverse events are any unfavorable or unintended sign (including abnormal laboratory findings), symptom or disease temporarily associated with the use of medical treatment or procedure regardless of whether it is considered related to the medical treatment or procedure (attribution of unrelated,

unlikely, possible, probable, or definite). Life-threatening adverse events are any adverse event that places the participant at an immediate risk of death from the reaction. Serious adverse events are any event occurring at any dose level that results in any of the following outcomes: death, a life-threatening adverse event, inpatient hospitalization, prolongation of an existing hospitalization, a persistent/significant disability/incapacity, and other medically significant events. Unexpected adverse events not listed above may also occur.

All observed or volunteered adverse events will be recorded on the Adverse Event form. Events involving adverse drug reactions, illnesses with onset during the study or exacerbation of pre-existing illnesses will be recorded. Objective test findings, such as abnormal lab values, that result in drug dosage changes will also be recorded.

6.8 Adverse Event Reporting

Adverse events will be graded according to the Cancer Therapy Evaluation Program's; Common Terminology Criteria for Adverse Events Version 4 (CTCAE), which can be downloaded from <http://ctep.cancer.gov>. A severity grading of side effects related to Lovastatin use can be found in Appendix 7. The principal investigator at each site will determine whether the adverse event is related or unrelated to the medical treatment. If deemed to be related, the principal investigator will determine whether the adverse event is expected or unexpected. Details of the event (expected or unexpected), and whether the side effect and severity (i.e. toxicity) were included in informed consent (yes/no), will be recorded on the adverse event module form.

A justification will be recorded on the adverse event module if the observed toxicity was not included in the informed consent. For all adverse events, the investigator must pursue and obtain information to determine the outcome of adverse events and to assess whether it meets the criteria for classification of a serious adverse event. All serious adverse events require immediate notification to the Operations Center. All adverse events, whether serious or otherwise, will be followed until resolution (the patient's health has returned to his/her baseline status) or until the event has stabilized (investigator does not expect any further improvement or worsening of the adverse event). Participants withdrawn from the study due to adverse events will be followed by the investigator until resolution. All grade 3, 4 and 5 adverse events will be reviewed by the Clinical Review Committee.

All adverse events will be tabulated by treatment arm, severity grade and reported to the NF1 Data and Safety Monitoring Board (DSMB). The occurrence of adverse events will be reviewed by the DSMB at 2-month intervals to monitor patient safety. Summary details of the occurrences and grade of adverse events will be distributed to each site at 2-monthly intervals. It will be the responsibility of the site principal investigator to disclose this information to the site's institutional review board. In addition, all unexpected and serious adverse events will be forwarded to the medical monitor, [name]. She will serve as a patient advocate, will be independent of the clinical study team, and will report to the DSMB. She will oversee the progress of the protocol, especially issues of individual subject/patient management and safety. The monitor will provide an unbiased written report of each event.

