2.3 Hypotheses

It is hypothesized that Lovastatin will improve the visual spatial memory and/or attention deficits in children with NF1. This is based on studies demonstrating that Lovastatin has significantly improved impairments in visual spatial memory and attention in the NF1 murine model.

It is further expected that Lovastatin will be safe and well tolerated over a 16-week period.

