APPENDIX 3: Study Evaluation Before, During, Post Treatment and Follow-Up

Observation	Pre-treatment	2 weeks*	4 weeks (2 titrated & 2 weeks full dose)	8 weeks	12 weeks	Post-treatment 16 weeks	Follow-up (8 weeks off medication)
Phone Calls		X					
Hx and Physical	X		X	X	X	X	X
CBC	X		X	X	X	X	X
Chemistries	X		X	X	X	X	X
Neuropsychological measures	X					X	X
Pregnancy testing	X			X		X	
Side-Effects/Toxicity (Check List)		X	X	X	X	X	X
Drug compliance		X	X	X	X	X	

NB. Chemistries: Blood urea nitrogen (BUN), creatinine, glucose, alanine amino transferase (ALT), aspartate amino transferase (AST), total and direct bilirubin, CPK, Lipid profile (HDL, Cholesterol, LDL, Triglycerides). Indirect bilirubin will be computed from total and direct bilirubin serum measurements.

*Use CRFs as a guide with questions for phone follow-up

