APPENDIX 10: Adverse Event Monitoring – UK Sites

Participants will be monitored closely for medication side effects with a diary and with laboratory testing as indicated in the Study Procedures section (see of the protocol (see Section 5). Adverse events will be addressed immediately. Participants will also be closely followed clinically at least once per month while on the study medication by the site physician. The Side Effects Checklist and Adverse Event Monitoring Form will be used to assess participants at every visit or phone contact.

An adverse event is the appearance or worsening of any undesirable sign, symptom, or medical condition occurring after the study has commenced, even if not considered to be related to the investigational medicinal product. Medical conditions/diseases present before starting the study will only be considered as adverse events if they worsen after the start of the study. Abnormal laboratory values or test results constitute adverse events only if they induce clinical signs or symptoms, are considered clinically significant, require therapy, or as specified on CTCAE, version 4.

The occurrence of adverse events will be sought by non-directive questioning of the patient during the study. Adverse events also may be detected when they are volunteered by the patient or through physical examination, laboratory test, or other assessment. As far as possible each adverse event will be evaluated to determine:

1. The severity (mild, moderate, severe)
2. Its relationship to the investigational medicinal product
3. Its duration
4. Action taken (no action taken; study drug dose adjusted/temporarily interrupted; study drug permanently discontinued; concomitant medication taken; non-drug therapy given; hospitalisation required)
5. Whether it is **serious**, where a serious adverse event (SAE) is defined as one which:
 - Is fatal or life-threatening
 - Results in persistent or significant disability/incapacity
 - Constitutes a congenital anomaly/birth defect
 - Requires prolonged hospitalisation (except where it is for routine treatment/monitoring, elective or pre-planned treatment not related to study, for social or respite reasons)
 - Is medically significant i.e. defined as an event that jeopardises the patient or may require medical or surgical intervention to prevent one of the above

Unlike routine safety assessments, SAEs are monitored continuously and have special reporting requirements (see below).

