All adverse events will be tabulated by treatment arm, severity grade and reported to the US NF1 Data and Safety Monitoring Board (DSMB). The occurrence of adverse events will be reviewed by the DSMB at 2-month intervals to monitor patient safety. Summary details of the occurrences and grade of adverse events will be distributed to each site at 2-monthly intervals. In addition, all unexpected and serious adverse events will be forwarded to the US medical monitor, [name]. She will serve as a patient advocate, will be independent of the clinical study team, and will report to the DSMB. She will oversee the progress of the protocol, especially issues of individual subject/patient management and safety. The monitor will provide an unbiased written report of each event.

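### The only by-arm adverse-event table sets no on-treatment window and does not separate the 16 weeks on drug from the 8 weeks off drug

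*Protocol*

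**What the plan says.** **Aim and period.** Aim 2.2.2 of the protocol is to evaluate toxicity and tolerability. Section 2.3 gives the hypothesis a period: "It is further expected that Lovastatin will be safe and well tolerated over a 16-week period". Section 3.1 bases the safety evaluation on laboratory tests, clinical signs and adverse effects, and places their monitoring within the 16 weeks.

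**Collection.** Section 6.7 goes further: "Participants will be monitored for adverse events regularly throughout the study", and "Events involving adverse drug reactions, illnesses with onset during the study or exacerbation of pre-existing illnesses will be recorded". The side-effects checklist is used at every visit or phone contact. Appendix 3 marks it in the column headed "Follow-up (8 weeks off medication"), a visit that section 5.4 places 8 weeks (± 7 days) after treatment stops.

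**Definition.** Section 6.7 describes an adverse event as a sign, "symptom or disease temporarily associated with the use of medical treatment or procedure regardless of whether it is considered related". That links it to treatment in time but gives no number of days. For UK sites, Appendix 10 says: "An adverse event is the appearance or worsening of any undesirable sign, symptom, or medical condition occurring after the study has commenced", with no end point.

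**Tabulation.** Section 6.8: "All adverse events will be tabulated by treatment arm, severity grade and reported to the NF1 Data and Safety Monitoring Board (DSMB"). Appendix 10 repeats the rule: "All adverse events will be tabulated by treatment arm, severity grade and reported to the US NF1 Data and Safety Monitoring Board (DSMB").

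No section defines an on-treatment window, asks for a split by period, or gives an exposure-adjusted rate. SAP section 7.0 contains no safety analysis. The only post-dose limit is the 30 days in protocol section 6.10, which concerns expedited reporting of deaths and is not a tabulation rule.

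**The concern.** The hypothesis covers 16 weeks, but the table takes every event over about 24. In the last 8 weeks neither arm takes study drug. Section 6.5.1 says that reported side effects have been considered reversible once the drug is stopped, so on the protocol's own premise those weeks contribute mainly background complaints to both arms.

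Headache, fatigue, abdominal pain and muscle pain are listed effects of lovastatin and are also everyday complaints in children. For such events, adding off-drug background makes the comparison of arms less sensitive to a real on-drug excess. Common, expected grade 1 and 2 symptoms are affected most, because this table is the only place where they are compared between arms. An unstated window can also be chosen after the data are unblinded.

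**Working it through.** **The plan's own figure.** The documents give no adverse-event rate, window or power, so the only design figure to reproduce is the efficacy sample size, which is not in dispute. For 0.5 SD, two-sided 0.05 and power 0.80, the normal approximation gives 63 per arm. The t-test gives 63.8, so 64 (power 0.801). Allowing 10% dropout, 128/0.9 = 142.2, stated as 142, or 71 per arm with equal allocation.

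**Inputs from the protocol.** 16 weeks on drug (section 3.1); 8 weeks off drug (section 5.4); checklist contacts at weeks 2, 4, 8, 12 and 16 on drug and one off drug (Appendix 3).

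**Assumptions, not in the documents.** A constant background rate λ per week in both arms; a lovastatin rate ratio R while on drug and 1 after stopping; the background risks used below.

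**Rate ratio, equal capture in both periods.** Pooled ratio = (16R + 8)/24.
- R = 1.5: (24 + 8)/24 = 1.33
- R = 2.0: (32 + 8)/24 = 1.67
- R = 3.0: (48 + 8)/24 = 2.33

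One third of the excess over 1 is lost.

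**Rate ratio, capture in proportion to scheduled contacts.** Pooled ratio = (5R + 1)/6. For R = 2.0 this is (10 + 1)/6 = 1.83.

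**Excess event count.** At R = 2.0, expected events per child are 32λ against 16λ on drug, and 40λ against 24λ over 24 weeks. The difference is 16λ both times.

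**Children with at least one event.** Let p be the placebo risk over 16 weeks. With equal capture and R = 2.0:
- on drug: placebo p, lovastatin 1 − (1 − p)^2
- over 24 weeks: placebo 1 − (1 − p)^1.5, lovastatin 1 − (1 − p)^2.5

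For p = 0.20 these give 0.200 against 0.360 on drug, and 0.284 against 0.428 over 24 weeks. The power column uses 71 per arm and two-sided 0.05. It is illustrative only, because no adverse-event test is planned.

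| Placebo risk in 16 weeks | Risk difference (points), 16 wk vs 24 wk | Risk ratio, 16 wk vs 24 wk | Power, 16 wk vs 24 wk |
|---|---|---|---|
| 5% | 4.7 vs 4.6 | 1.95 vs 1.63 | 0.19 vs 0.15 |
| 10% | 9.0 vs 8.5 | 1.90 vs 1.58 | 0.33 vs 0.25 |
| 20% | 16.0 vs 14.3 | 1.80 vs 1.50 | 0.57 vs 0.43 |
| 40% | 24.0 vs 18.6 | 1.60 vs 1.35 | 0.82 vs 0.63 |

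**The case against.** The strongest reply is that nothing in the documents says the two periods will be merged. Section 6.8 is a reporting instruction to the DSMB, and a table split by period would also satisfy it. Section 7.0 leaves the content of interim analyses to the DSMB, section 8.1 leaves the content of safety reports to the External Advisory Board, and sections 2.3 and 3.1 point toward a 16-week evaluation. This stands in part: pooling is what the rule produces if followed literally, not a declared intention. But nothing requires a split, and no other by-arm safety analysis is given for aim 2.2.2.

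It is also fair to say that the effect is limited. Attribution is recorded for each event. Serious and unexpected events go individually to the medical monitor, and grade 3 to 5 events to the Clinical Review Committee. A child's off-drug events can reach the two-monthly DSMB review only after that child's week 16. With one scheduled contact off drug, fewer background events may be captured. The off-drug weeks may also show delayed or persistent toxicity, so they should not be discarded. All of this stands, and it limits the size of the problem without supplying a window.

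A reader might infer that children who stop early worsen the mixing by adding off-drug time. The documents do not support this. Sections 5.2.3 and 6.6 take such children off the study or protocol, section 6.8 follows those withdrawn for adverse events until resolution, and nothing says that new events are collected from them to week 24.

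**Conclusion.** The point holds as a gap in the analysis rule. The only by-arm adverse-event table, read as written, does not separate time on drug from time off drug, although the hypothesis concerns the 16 weeks. The consequence is a less sensitive comparison on the ratio scale: a true rate ratio of 2.0 would show as roughly 1.67 to 1.83, depending on how fully off-drug events are captured. This rests on constant background rates and no drug effect after stopping. The second assumption is supported by section 6.5.1 but is not established for this trial, which itself looks for carry-over.

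A reader might go further and infer that the table would hide lovastatin toxicity in general, or that it biases the trial toward finding the drug well tolerated. The documents do not support that. The expected excess in events is the same with or without the off-drug weeks, and the risk difference for uncommon events hardly changes (4.7 against 4.6 points at 5% background). The more serious events are reviewed case by case. The loss is mainly in ratios, and in risk differences for common complaints.

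**What to change.** In protocol section 6.8, Appendix 10 and the SAP, add text to this effect:

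> Adverse events will be tabulated by arm and worst grade, as the number of children with at least one event, separately for (a) the on-treatment window, from first dose to last dose plus a lag stated before unblinding, and (b) the remaining off-drug period to the follow-up visit. The toxicity comparison for aim 2.2.2 is based on (a). Table (b) and the total over all events are shown alongside.

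A lag is needed because a window closing on the last dose would exclude an event that starts just afterwards.

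Confirm that the adverse-event form records onset dates. Section 6.8 does not name them among the details recorded, and Appendix 10 asks for duration.

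The cost is slightly more table programming. The choice of lag will move a few events between the two tables, which is why both are shown. No dose, visit or clinical rule changes.
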